5. LIST OF ABBREVIATIONS

6. PROTOCOL SUMMARY

Full Title: Systemic Effect of Lycosome-Formulated Dark Chocolate and GA Lycopene on Gut Microbiota, Liver Metabolism, Blood Markers of Oxidative Status and Skin Parameters in Healthy Overweight Volunteers

Short Title: Effect of Lycosome-Formulated Dark Chocolate and Lycopene on Gut Microbiota, Liver, Blood and Skin

Sample Target Size: 30

Study Population: Healthy Caucasian males and females with no acute or chronic diseases aged from 50 to 70 years with body mass index more than 30 and less than 35 kg/m².

Participating Sites:

1. Lycotec Ltd, [name]. [contact] [contact]
2. Institute of Cardiology, [name], Russia

Study Design:

The study is designed as a single, interventional, randomized clinical study to determine if one month's consumption of lycosome-formulated dark chocolate (DC) containing lycopene affects the spectrum of intestinal microbiota, blood lipids, liver parameters and oxidative status of healthy volunteers. The effects of lycopene alone and DC without lycopene addition are in the scope of the control groups as secondary objectives. All volunteers will be asked to give written consent to participation in the study and will be informed about the major goal of the study and its objectives.

The major research question to be answered in the study is whether ingestion of lycosome formulated DC or its two major constituents – lycopene and cocoa flavanols for 1 month can affect the composition of the gut microbiota, liver metabolism, blood markers of biological oxidation and skin parameters in healthy middle-aged overweight individuals.

Therefore, the primary endpoint of the project will be parameters reflecting composition of gut microbiota, blood lipids and markers of serum levels of biological oxidation – malonic dialdehyde, oxidized LDL and certain other values. The secondary endpoints will be skin parameters – sebum, corneocytes and bacterial load. Each of these parameters will be measured before trial initiation ("0" time point) and after 1 month (final point of clinical study).

The study will be conducted following enrolment of 30 volunteers with equal representation in the study population of males and females. The study is planned to include healthy overweight individuals in the age range of 50 to 70 years old, with confirmed health status and no indication of chronic or acute disease. In particular, volunteers with history or immediate signs of

liver disease, alcoholism or intake of any medication (non-steroidal anti-inflammatory drugs, hormones, vitamins and food supplements or energy drinks) will be excluded from participation in the study. Among other exclusion criteria will be pregnancy, extensive tobacco smoking (>10 cigarettes per day), and history of cardiovascular disease. To minimize inconsistencies originating from body weight, patients with Body Mass Index (BMI) from 30 to 35 will be enrolled in the study. All volunteers will be requested to withdraw from consumption of dark chocolate, cocoa and lycopene containing products (tomatoes, ketchup etc.) for 2 weeks prior to study initiation and will be requested to ingest cocoa and lycopene-containing products strictly as mandated by the study protocol.

All study participants will undergo a preliminary anamnestic and clinical investigation. This will include reading the vital signs, determination of body mass index, anthropometry, blood pressure measurement, and electrocardiography. Among the laboratory tests will be determination of fasting serum glucose and lipids (total cholesterol, LDL cholesterol, HDL and total triglyceride levels), determination of ALT and AST level, total bilirubin, and CRP. All volunteers will be also be subject to a standard hematological investigation.

The volunteers will be randomized according to age, gender, body weight and BMI using a simple randomization method and block randomization.

The interventional procedure will be conducted stringently according to the conditions described in the protocol approved by the Institutional Review Board. In particular, volunteers will be given the study products over two separate visits for a total of one month's supply. To assess effect of lycosome-formulated DC volunteers from the first arm will be given lycosome-formulated DC containing 7mg lycopene while volunteers from the fifth arm will be given the regular formulation of DC without lycopene. Volunteers from the second arm of the study will be given capsules containing 7 mg of lycopene, this amount is equal to the amount of lycopene ingested daily with lycosome-formulated DC. Investigational products will be given to volunteers twice – at the "0" time point of the study and at the intermediate time point (two weeks after study initiation). To assess dose-dependency and effect of fat matrix volunteers from the third and fourth arms will be given 30 mg of lycopene in either cocoa butter or sunflower oil.

Upon arrival at the study site all volunteers will be asked about current health status and will undergo scrupulous anamnestic, physical and laboratory investigations. Each of these procedures will be conducted by

highly trained medical professionals including nurses and practicing physicians.

Study products will be given immediately after all evaluations are complete.

Lycosome formulation of DC is a proprietary formulation of DC (Lycotec Ltd, Cambridge, UK) with enhanced bioavailability of lycopene and cocoa flavanols in which the flavanols are protected from oxidation by a lycopene coat and embedded into cocoa butter micelles of the chocolate matrix preserving thereby cocoa flavanols from degradation and oxidation. The final concentration of lycopene in 10 grams of the composite lycosome formulation of DC is 7 mg. The lycopene is in the form of tomato oleoresin from Lycored Inc. (NJ, USA) and contains 97% all trans-isomers and 3% all cis-isomers.

Volunteers will be asked to consume the investigational products in the evening with the main meal once a day for 1 month.

Blood serum specimens will be collected, processed, aliquoted and frozen at – 80°C for later analysis at both the “0” time point of the study and after 1 month of the study. All aliquots will be coded without the name of the volunteer being indicated. The identity of specimens will be known only to the Principal Investigator and the Medical Monitor.

Fecal specimens will be collected at the same time points by volunteers in the comfort of their homes and will be required to be delivered to the study laboratory within 1 hour of collection. All fecal specimens will be frozen and stored at the study site until analysed. Should any shipping be required the study specimens will be shipped on dry ice by overnight courier.

Among the biochemical tests conducted on serum specimens will be the activity of liver specific enzymes (alanine aminotransferase and aspartate aminotransferase as well as activity of gamma-glutamyltransferase), level of bilirubin, concentrations of triglycerides, LDL, HDL, total cholesterol and levels of peroxidation products (IOD and LDL-Px).

Biochemical assays will be performed by qualified and licensed personnel using a BioSystems Analyzer and compatible commercial kits of reagents. Standards will be purchased from Sigma-Aldrich only.

Skin swab parameters will be assessed on sebum quantity and viscosity, rate of corneocyte desquamation and damage, and total bacterial load of gram-negative bacteria.

[figure not shown]
Encoding of the results will be performed in collaboration with the Principal Investigator and the Medical Monitor.

[figure not shown]
Statistical analysis will be performed by an independent statistician using commercially available “BioStat-3” software. The statistician will not be informed of study group names or the nature of interventions in each group.

Packaging and labeling of study products and biological specimens will be carried out according to the guidelines of the NIH and US Department of Health and Human Services, as recommended for biologicals and investigational health food products. The study products will be shipped to the study site in specially designed containers with primary and secondary components. A container closure system will be used to avoid contact of investigational products with light, moisture, excess temperature and air. This packaging system guarantees stability of the products for the intended use. Protection from microbial contamination is provided by maintaining container integrity after the packaging system has been sealed. An adequate and validated procedure will be used for investigational product manufacture and packaging.

All individual packages of lycosome-formulated DC and regular DC as well as lycopene capsules will be labeled with a numerical code. None of the volunteers or study personnel will be informed about coding assignment for the duration of the study.

Study Scheme

Upon arrival at the study site the investigational products will be inspected by the Medical Officer and stored in a locked room at the study site. Only the Medical Officer and Principal Investigator will have access to the investigational products during the study.

Results collected for each volunteer will be stored as both paper files and digital files in Excel format and will be available for access by the Medical Officer and Principal Investigator. To avoid bias each volunteer will be given a random computer code containing numerical characters and three letters.

7. Clinical Protocol

7.1 Introduction:

7.1.1 Background:

The human gastrointestinal (GI) tract contains a complex and dynamic population of microorganisms widely defined as the gut microbiota, which exert a notable influence on the host in health and disease (1). Multiple factors contribute to the establishment and diversity of the human gut microbiota. Diet is considered as one of the main factors

controlling and shaping the gut microbiota throughout life. Intestinal bacteria play a crucial role in maintaining immune and metabolic homeostasis and protecting against pathogens and toxic products of intermediate metabolism, including free radicals (2). Altered gut bacterial composition (dysbiosis) has been associated with the pathogenesis of many inflammatory diseases, infections and possibly biological oxidation (3). The interpretation of these studies relies on a better understanding of inter-individual variations, heterogeneity of bacterial communities along and across the GI tract, functional redundancy and the need to distinguish cause from effect in states of dysbiosis. Our current understanding of the development and composition of the human GI microbiota is that it is highly affected by nutritional factors and impacts the integrity of metabolic pathways in extra-intestinal tissues throughout the body as well as the processes of biological oxidation.

The human GI tract is the largest interface structure (250–400 m²) in the human body and protects the host from foreign substances and organisms including bacteria, viruses, environmental factors and antigens (4). Over the human lifespan around 60,000 kg of food passes through the human GI tract, along with an abundance of microorganisms from the environment which impose an enormous challenge to gut structure and function (4, 5). The variety of intestinal bacteria in the GI tract termed the 'gut microbiota' helps prevent damage and has co-evolved with the host throughout evolution to form an intricate and mutually beneficial relationship (3, 6). The number of microorganisms inhabiting the GI tract has been estimated to exceed 10¹⁴ which represents about 10 times more bacterial cells

than the number of human cells and over 100 times the amount of genomic content (microbiome) as the human genome (1, 7). Carbohydrate fermentation is one of the main activities of the human gut microbiota, driving the energy and carbon turnover of the colon. Dominant and prevalent species of gut bacteria, including short-chain fatty acid (SCFA) producers, appear to play a critical role in initial degradation of complex plant-derived polysaccharides (8). Other gut bacteria are known to specialize in oligosaccharide fermentation, in particular Bifidobacteria. Supplementary species are known to participate in reductive acetogenesis, reduction of sulfate and methanogenesis (8, 9). Efficient conversion of complex indigestible dietary carbohydrates into SCFA is essential for the nutritional requirements of gut microbial populations as well as for colonic cells which use SCFA for energy requirements (10). Moreover, butyrate and propionate produced by the gut microbiota are essential for intestinal physiology, immune function and possibly mitochondrial respiration, while acetate acts as a substrate for lipogenesis and gluconeogenesis in eukaryotic cells (11). SCFA have also been shown recently to be involved in regulation of immune function, all stages of inflammation and adipose tissue function (12). A wide spectrum of inflammatory mediators regulated by gut microbiota function are essential for adipose tissue function in obesity and type 2 diabetes mellitus (13). The proximal colon is a major site of carbohydrate conversion by the gut microbiota (14). Depletion of carbohydrate content in the distal colon promotes switching of digestive conversion to other substrates, in particular proteins and fat remnants. Their catabolites - ammonia, phenols, p-cresol, certain amines and hydrogen sulfide are highly toxic substances whose accumulation in the colonic lumen may provoke inflammation and cancer (15). Therefore, function

of the gut microbiota is mediated mainly by chemical messengers and metabolites whose production is highly dependent on diet and food constituents.

7.2 Rationale:

Diet and other environmental factors are essential in modulating the composition and metabolic activity of the human gut microbiota, which in turn has a serious impact on health. In particular, macronutrients have a major role in shaping the composition and activity of these complex populations of gut microbiota. It is widely accepted that carbohydrates play the most important role in regulating the microbiota spectrum. The impact of dietary fats on the gut microbiota is less well defined. Western-style diets, rich in fat and proteins, are associated with gut microbial populations that are typified by a *Bacteroides* enterotype whereas traditional diets rich in plant polysaccharides and carbohydrates are associated with a *Prevotella* enterotype. Vegetarian dietary patterns are more likely associated with an abundance of *Clostridium* clusters (16).

It is suspected that dietary polyphenols sourced from many foods including grapes, grains, tea, cocoa and berries, may have some impact on gut microbiota (17). However, there are no systematic studies devoted to this question. Similarly, the effect of DC on the gut microbiota remains largely unknown. It is completely unknown for now whether lycopene, a major carotenoid from tomatoes, may have any effect on intestinal bacteria. Moreover, the relationship between the intestinal microbiota and biological oxidation systems has never been investigated.

It has to be emphasized that use of cocoa-derived polyphenols and lycopene in clinical studies is a very challenging task. Each of them has

a low bioavailability rate due to the hydrophobic nature of their amphiphilic molecules. Therefore, clinical studies aimed at the investigation of biological functions of lycopene and cocoa flavanols may require special nutraceutical formulations of these compounds with enhanced bioavailability. A newly developed lycosome formulation of DC (Lycotec Ltd, Cambridge, UK) contains both lycopene and cocoa flavanols in highly bioavailable forms (18). This formulation was developed by implementation of different microencapsulation techniques (spray drying, ultrasound, supercritical CO₂) which allows incorporation of bioactive compounds (lycopene and cocoa flavanols in this particular case) into the structure of lycosomes which are particles with an increased resistance to the acidic environment of the stomach and higher ability to be absorbed in the intestine (19). Besides the compounds of interest (lycopene and cocoa flavanols), lycosome particles (coco-somes) contain a phosphatidylcholine (used as a hydrophilizing and emulsifying agent).

Moreover, the lycopene used in lycosome-formulated DC is a well known antioxidant whose anti-radical capacities exceed the anti-radical capabilities of all other carotenoids multifold (20). Therefore, ingestion of lycosome-formulated DC may translate into significant attenuation of free radical formation in the human body. This creates the rationale to investigate parameters of biological oxidation in volunteers ingesting lycosome-formulated DC.

Altogether the factors mentioned above support the main objective of our study, creating a rationale for trying to investigate the effect of lycosome-formulated DC on microbiota spectrum and oxidation processes in healthy volunteers.

Each of these questions will be addressed in the current study.

7.3 Clinical Study Objectives:

7.3.1 Primary objective:

The primary objective of this clinical study is to verify the effect of lycosome-formulated dark chocolate (DC) and its two major ingredients – lycopene and cocoa flavanols on the spectrum of gut microbiota in healthy middle-aged overweight volunteers.

Secondary objective:

To investigate the effect of lycosome formulated dark chocolate (DC) and its two major ingredients – lycopene and cocoa flavanols on liver metabolism, blood lipids, marker of oxidative and inflammatory damage, and skin parameters in healthy middle-aged overweight volunteers.

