7.4.6 Mode of intake

The volunteers will be asked to take the study products, one 10 gram bar of lycosome formulated DC, 1st arm, or one 10 gram bar of regular DC, containing no lycopene, 5th arm, once a day in the evening with the main meal for 1 month.

Volunteers from the 2nd arm of the study will be requested to take a capsule containing 7 mg of lycopene, an amount equal to the quantity of lycopene in the 10 g bar of lycosome formulated DC.

Volunteers in the 3rd arm will be asked to take capsules with 30 mg lycopene in cocoa butter, and in the 4th arm 30 mg of lycopene in sunflower oil.

All interventional products are to be ingested once a day in the evening with the main meal for 1 month.

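### No described arm is free of both lycopene and cocoa, so the effects named in the objectives have no randomised comparison, and the dose contrast depends on a carrier the readable text does not give

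*Protocol*

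**What the plan says.** The primary objective (Protocol 7.3.1) reads "The primary objective of this clinical study is to verify the effect of lycosome-formulated dark chocolate (DC) and its two major ingredients", which it names as lycopene and cocoa flavanols, on gut microbiota. The secondary objective uses the same form, "To investigate the effect of lycosome formulated dark chocolate (DC) and its two major ingredients", for liver metabolism, lipids, oxidative and inflammatory markers and skin.

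The arms are set out in sections 6 and 7.4.6:

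- Arm 1: "volunteers from the first arm will be given lycosome-formulated DC containing 7mg lycopene".
- Arm 2: "Volunteers from the 2nd arm of the study will be requested to take a capsule containing 7 mg of lycopene". The readable text names no carrier.
- Arms 3 and 4: "Volunteers in the 3rd arm will be asked to take capsules with 30 mg lycopene in cocoa butter, and in the 4th arm" the same amount in sunflower oil.
- Arm 5: "one 10 gram bar of regular DC, containing no lycopene, 5th arm".

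Section 6 gives arms 3 and 4 a further purpose: "To assess dose-dependency and effect of fat matrix volunteers from the third and fourth arms will be given 30 mg of lycopene", in cocoa butter or sunflower oil. It also says "The effects of lycopene alone and DC without lycopene addition are in the scope of the control groups as secondary objectives", so the reference groups are themselves lycopene alone and chocolate alone.

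The Study endpoint paragraph of the statistics section plans paired and unpaired t-tests and a Wilcoxon-Mann-Whitney test between groups. Section 6 has volunteers stop their own cocoa and lycopene-containing foods two weeks before the start, and take such products on study only as the protocol mandates.

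**The concern.** To say that an ingredient has an effect, one needs arms that differ in that ingredient and in nothing else that matters, or a product-free arm to show what would have happened anyway. The protocol describes neither for lycopene, flavanols or the lycosome bar as a whole. That leaves the paired test within an arm, which credits the product with any change over the month.

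At stake is the report's main conclusion. As the objectives stand, a significant paired test in arm 2 or arm 5 could be reported as showing that lycopene or flavanols alter the microbiota, with no randomised comparison behind it. Objectives and arms are fixed in the protocol, so a statistical analysis plan could not supply the missing comparison.

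**Working it through.** This is a question of what the arms identify, so the check is algebraic. The protocol's sample size of 30 comes with no effect size, standard deviation or power; it plays no part here and no sample-size error is asserted.

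**Components of the mean change in an arm** (additive model, an assumption that favours the plan):

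- mu: change over the month with no study product (time, diet restriction)
- L7, L30: lycopene 7 mg, 30 mg
- DC: chocolate, meaning flavanols plus everything else in the bar
- F: lycosome formulation. Section 6 says it raises the bioavailability of both ingredients, and section 7.2 adds phosphatidylcholine, so it cannot be taken as inert
- CB, SO: cocoa butter and sunflower oil carriers
- C2: carrier of the arm 2 capsule

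**Arm means**

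| Arm | Mean change |
|---|---|
| 1 | mu + L7 + DC + F |
| 2 | mu + L7 + C2 |
| 3 | mu + L30 + CB |
| 4 | mu + L30 + SO |
| 5 | mu + DC |

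There are five means and eight unknowns, and the matrix has rank 5. A quantity is estimable only if it is a weighted sum of the five rows.

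**What the arms identify**

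- Arm 1 − arm 5 = (mu + L7 + DC + F) − (mu + DC) = L7 + F
- Arm 1 − arm 2 = (mu + L7 + DC + F) − (mu + L7 + C2) = DC + F − C2
- Arm 3 − arm 4 = CB − SO

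**What they do not identify**

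- Lycopene, L7: it occurs only in arm 1, always with F, and in arm 2, always with C2. Removing F and C2 gives both arms weight zero.
- Chocolate, DC: removing F leaves only arm 5, which carries mu.
- Total effect of lycosome chocolate, L7 + DC + F: it needs arm 1 with weight 1, and no other arm can cancel mu without bringing in another component.
- Dose, L30 − L7: arm 3 − arm 2 = (L30 − L7) + (CB − C2), and arm 4 − arm 2 = (L30 − L7) + (SO − C2).

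**How far favourable assumptions go**

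| Assumption | L7 | DC | Dose |
|---|---|---|---|
| As written | no | no | no |
| F = 0 | yes | no | no |
| C2 = CB, or C2 = SO | no | no | yes |
| mu = 0 (before-after change taken as effect) | no | yes | no |
| All carriers 0 and F = 0 | yes | yes | yes |
| All carriers 0 and mu = 0 | yes | yes | yes |

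The protocol supports neither of the last two rows: it sets out to study the fat matrix, presents the formulation as active, and has no arm that shows mu is zero. Even where DC is estimable, it is the whole bar. No arm has chocolate without flavanols, so flavanols alone are not isolated under any row.

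**The case against.** The strongest reply is that active comparators are a legitimate choice. If the question is what the lycosome product adds to ordinary dark chocolate, arm 5 is a sensible randomised control, and section 6 describes lycopene and formulation as joined by design. Between-group tests are planned, and listing each contrast is commonly left to an analysis plan that is not shown. This stands as a defence of arm 1 v 5. It does not rescue the objectives, which name effects of the ingredients themselves.

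Four stronger readings might be inferred, and the documents do not support them.

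- *Dose-dependency has failed outright.* The aim appears in section 6, not in the 7.3.1 objectives. The study scheme is not shown, and a carrier that cannot be read is not a missing one. If arm 2 shares a carrier with arm 3 or arm 4, one dose contrast is clean. Using two carriers at 30 mg is what makes the fat-matrix question answerable.
- *Arms 3 and 4 will be pooled against arm 2.* The protocol plans no such pooling.
- *Before-after change is inflated by regression to the mean after re-screening.* That needs selection on extreme values of an outcome. Eligibility rests on age, BMI, health and medication; no threshold for microbiota, lipids or oxidation markers is stated.
- *The start of the diet restriction falls between the two measurements.* It begins two weeks before baseline, so only its continuing effect, and time, enter the change.

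**Conclusion.** The point holds in limited form. Three effects named in 7.3.1 (total lycosome chocolate, lycopene alone, flavanols alone) have no randomised comparison among the five arms described and rest on within-arm change. Three comparisons are valid for narrower questions: arm 1 v 5, arm 1 v 2 and arm 3 v 4. The dose-dependency aim is conditional on the arm 2 carrier and should not be counted as a failure until that is known.

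This assumes that the five numbered arms in the text are all the arms, and that carrier and formulation may affect the outcomes, as the protocol itself suggests. The additive model is the lenient case; interactions between components would make separation harder.

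**What to change.** Restate section 7.3.1, and align section 6 with it, as the randomised contrasts the arms support:

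- arm 1 v 5: lycopene in lycosome formulation against regular chocolate;
- arm 1 v 2: the whole lycosome chocolate bar against the lycopene capsule at equal lycopene;
- arm 3 v 4: carrier at equal dose.

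Base conclusions on between-arm comparisons of change from the 0 time point. Report within-arm changes as descriptive, with no causal claim for lycopene or flavanols alone.

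State the carrier of the arm 2 capsule in 7.4.6. If it matches arm 3 or arm 4, limit the dose contrast to that arm. If it matches neither, say that dose and carrier cannot be separated and drop the dose-dependency claim from section 6.

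This changes wording only; no arm, product or dose is altered. The price is that the ingredient questions are narrowed rather than answered.
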